10.3.3. Baseline Visit

If the participant does not have time or wish to complete the baseline survey at the UDS visit, it will be scheduled for another time to be conducted by study staff by phone. We have included a copy of the Baseline Survey. Measures incorporated in this study were selected from the PhenX Toolkit version November 11, 2021, Ver 40.4 for screening and baseline demographic and substance use measures. The PhenX Demographics form (Hamilton et al., 2011) collects information about demographic characteristics of the participant, including age, ethnicity, race (in addition to AIAN), education, marital status, employment status, the number of children under the age of 18 residing in their household, and the same question from Phase 1 measuring the importance of being Native to the participant's identity. We will utilize an item from the PhenX

Toolkit that lists seven major categories of different substances including stimulants (e.g., methamphetamine, Adderall), cocaine/crack, marijuana, sedatives/tranquilizers, club drugs, hallucinogens and inhalants/solvents; and inquire about the past 30-day use of each. For each substance endorsed, we will use the TLFB to assess the days of use. We will ask how the participant used opioids (i.e., injections, pills, patches, lozenges), as [name] noted that their recovery experiences may differ depending on how they consumed opioids. We will collect information on OUD treatments the participant completed within 30 days before baseline, such as inpatient or outpatient services, individual or group support services, or Narcotics Anonymous. Data on substance use will be collected to characterize the sample at baseline (and again at follow-up) and to explore patterns of intervention engagement by substance use.

Based on feedback from the research team on the importance of spirituality in Native culture, the baseline survey will also include items from the World Health Organization's Quality of Life Spirituality, Religion, and Personal Beliefs (WHOQOL SRPB) scale to measure the participant's spiritual, religious, and personal beliefs and how they affect their quality of life (WHOQOL SRPB Group, 2006). Included in the PhenX toolkit (Hamilton et al., 2011), the WHOQOL SRPB was tested in a cross-cultural study and is highly correlated with psychological and social domains of Quality of Life. The items selected for the present study were based on a study that identified items with the strongest factor loadings in each facet of the WHOQOL SRPB (Skevington, Gunson, & O'Connell, 2013) as well as the study team's input on which items would be most relevant to the Facebook group. Five items from the WHOQOL SRPB were included: "To what extent does any connection to a spiritual being help you to get through hard times?" covers the *connection to the spiritual being* facet; "To what extent are you able to experience awe from your surroundings? (e.g., nature, art, music)" covers the *awe and wonder* facet and most of our MBRP content; "How much does spiritual strength help you to live better?" covers the *spiritual strength* facet; "To what extent do you have inner peace?" covers the *inner peace* facet; and "To what extent does faith give you comfort in daily life?" covers the *faith* facet. The five items will be scored on a five-point Likert scale ranging from 0=not at all to 4=an extreme amount. The total score will range from 0 to 20.

Finally, the baseline survey will include the K6 scale (Kessler et al., 2002) to characterize the sample at baseline and to monitor psychiatric symptoms at follow-up. Included in the PhenX toolkit (Hamilton et al., 2011), the K6 is a screening measure that assesses psychological distress including depressive and anxiety symptoms over the past month. The K6 measures distress with six questions (e.g., "How often did you feel nervous?" "How often did you feel hopeless?") scored on a five-point Likert scale ranging from 0=none of the time to 4=all of the time. Total scores can range from 0 to 24, with a recommended cutoff score of 13 to indicate the presence of a psychiatric disorder. The K6 scale is a widely used indicator of nonspecific psychological distress and is highly correlated with mental illness.

For individuals completing the baseline survey, the study staff will send the participant an invitation to the Facebook group by email or text message, depending on the participant's preference. If the participant does not have a Facebook account, we have included instructions that will be provided to participants on how to set one up. We developed these instructions for use in prior studies (Sinicrope et al., 2022).

Participants will receive a \$ [REDACTED] cash card for completing the baseline survey as a thank you for their time. Study staff will ask the participant to provide their mailing address for the [REDACTED] cash card, which the study staff will document in REDCap. This information will not otherwise be included in the dataset.

10.3.4. Enrollment

Eligible individuals providing written informed consent, completing the baseline survey, and accepting the invitation to join the Facebook group will be enrolled. Participants will be informed that the Facebook group will begin when all 10 participants have enrolled. The participant will be mailed or provided with a smudge kit and journal at the UDS visit to use for smudging and MBRP/SMART exercises posted to the Facebook group. The smudge kit is a bundle of cedar, sage, and sweetgrass inside an abalone shell approximately 2 to 3 inches in diameter, and it comes in a resealable travel bag.

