supporting recovery as an adjunct to treatment - a kind of continuing care via social support – was noted. Second, the intervention is group-based and delivered virtually without any in-person contact from the moderators. Thus, we want to ensure our participants are stable with respect to abstinence and currently receiving MOUD care to enhance the likelihood that they will engage with the Facebook group and to reduce potential adverse risks. Third, when co-designing the study concept for a social media intervention to support recovery with our AIAN community partners it was thought to be essential that women were connected to MOUD support, and that, as a treatment adjunct the proposed intervention could reinforce Native ways of knowing and cultural values to cope with stress and community resiliency for maintaining abstinence. Based on our community partner feedback it was also preferred that we did not restrict the duration of MOUD use at study enrollment so that the intervention could support MOUD initiation and continuation. Likewise, feedback from our CAC has reinforced this aspect of selecting our study population. The community-based participatory approach and working with our AIAN partner community clinics have been key to designing this study protocol and should enhance our recruitment efforts as well as all aspects of study implementation and dissemination. As the first step in this line of research, therefore, we chose to develop the intervention with a more homogenous sample of women who are abstinent from opioid use and receiving MOUD. Nonetheless, the intervention content could readily be expanded in future work for relevance to a broader population of Native women to encourage treatment-seeking and use of MOUD. In fact, our CAC discussed a pathway to later stages of the research to include Native women in recovery who can help to mentor other women to initiate abstinence within the same Facebook group.

We do not specify a maximum age limit. As discussed in the Background and Significance section, our prior work evaluating a Facebook intervention for nicotine use found a wide age range among participants. We will describe any patterns in intervention engagement by age to inform the refinement of the intervention and future research.

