consumed exceeds the prescribed amount. If they do not have a prescription, they will not be eligible for this study and will be provided referral resources.

The test will detect other commonly abused substances besides opiates, and the full results will be used to characterize the sample at baseline. Any other positive result besides opiates and opioids will be neither an inclusion nor exclusion criterion or outcome measure. Eligible participants may complete the baseline survey with the study staff immediately after the UDS during this visit, or it will be scheduled to be completed by phone in the near future. Participants will receive a \$50 cash card for completing the UDS as a thank you for their time and for any travel costs incurred.

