10.3.8 Follow-Up

Assessments will be conducted at the end of the intervention with a six-week visit window for completion (King et al., 2020). The participants will complete a UDS and a Follow-up Survey (by phone or in-person at the UDS visit). Study staff will attempt to contact the participant up to three times to complete the assessments and additionally reach out to the participant's secondary contact as needed. If the participant cannot be contacted within the six-week visit window, they will be considered lost to follow-up. Participants will receive a \$ [REDACTED] cash card for completing the Follow-Up Survey. They will receive an additional \$ [REDACTED] [REDACTED] cash card for completing the in-person UDS as a thank you for their time and for any travel costs incurred.

Follow-up Survey measures will evaluate treatment satisfaction and user experience using the Social Media Usability scale as well as four open-ended questions. It will also ask for the participant's thoughts on the potential for the group to be used as a way to encourage women to start their recovery journey and whether the participant would be interested in a peer moderator role for a future Facebook group. The TLFB will be used to assess opioid, opiate, and fentanyl use and MOUD use for each day since the previous TLFB assessment conducted at screening. We will again collect information on other OUD treatments the participant completed within the 30 days during the intervention. Using the TLFB, we will again assess for other substance use including stimulant use such as methamphetamines, cocaine/crack and marijuana use. The UDS

will be conducted in-person and staff will follow the same procedures as described above for the screening visit.

The Follow-Up Survey will include the same items from WHOQOL SRPB as the Baseline Survey to assess any changes in how their spirituality affects their Quality of Life and the K6 scale to assess changes in psychiatric symptoms during their participation in the Facebook group. It will also ask how important the participant feels it would be for Facebook groups like the pilot group to address spirituality from 0=not at all important to 10=very important. The study staff will assess adverse events (AEs) and serious adverse events (SAEs) including self-reported trips to the emergency department (ED), hospitalizations, and overdoses since enrollment.

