The research team will develop written intervention moderator guidelines for how often the moderator should log in, check-in and respond to comments/postings and other expectations for moderator engagement. A potential concern about using social media for health interventions is that user postings may be of poor quality, for example, inconsistent with clinical practice guidelines or involve inappropriate or illegal activities. When participants enter the study, they will be informed about the policies for posting content and that any inappropriate postings will be removed. The moderator will be trained to handle inappropriate or misinformation, and to direct information content toward evidence-based information exchange and social support. All study staff and volunteers will be required to complete and pass the CITI HIPPA/confidentiality course prior to any subject contact.

E. Management of Risks to Participants

Confidentiality

Confidentiality of participant records will be secured by use of study codes for identifying participants on CRFs, and secure storage of any documents that have participant identifiers on site, as well as secure computing procedures for entering and transferring electronic data. The documents or logs linking the study codes with the study participant on site will be kept locked/securely stored separately from the study files and records. No identifying information will be disclosed in reports, publications, or presentations.

Information That Meets Reporting Requirements

The consent form will specifically state the types of information that are required for reporting and that the information will be reported as required. These include suspected or known sexual or physical abuse of a child or elders or threatened violence to self and/or others.

Participant Protection

The site's study clinician or other designated and qualified individual will evaluate all pertinent screening and baseline assessments prior to participant enrollment to ensure that the participant is eligible and safe to enter the study. AEs will be assessed and documented at each study visit. Individuals who experience an AE that compromises safe participation in a study will be discontinued from further intervention and provided referrals for other treatment or to specialized care. Study personnel will request that the participant complete an end-of-intervention visit to assure safety and to document end-of-intervention outcomes.

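### Women are assessed one at a time but the group opens only when the tenth has enrolled, so K6 and spirituality change includes an unequal wait that no rule limits

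*Combined protocol and SAP*

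**What the plan says.** Sections 10.3.1 to 10.3.3 take each woman separately through the phone screen, the clinic visit (UDS, suicidality questions, MOUD check) and the baseline survey. The survey need not wait: "Eligible participants may complete the baseline survey with the study staff immediately after the UDS during this visit". Otherwise it is done later by phone. Section 10.3.3 continues: "For individuals completing the baseline survey, the study staff will send the participant an invitation to the Facebook group". Section 10.3.4 makes enrollment depend on consent, the survey and acceptance of that invitation, and then sets a common start: "Participants will be informed that the Facebook group will begin when all 10 participants have enrolled".

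The assessment table in section 10.3.9 has only Time 1 and Time 2. Section 10.3.8 repeats the spirituality items to look for change and uses "the K6 scale to assess changes in psychiatric symptoms during their participation in the Facebook group". Under section 11.2 a substantial K6 rise from baseline prompts clinician follow-up, and under section 18.19.1 deterioration on the K6 is a reportable adverse event that staff assess for relation to the intervention.

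The follow-up TLFB covers every day from screening (section 10.3.8). Relapse is counted over either the last 30 days or the time from enrollment, with no choice made between them (sections 7.3 and 17.3.2.3). The Protocol Summary and section 6.3 put Phase 3 participation at about two months.

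On the kit, section 10.3.4 says: "The participant will be mailed or provided with a smudge kit and journal at the UDS visit". Section 10.1.1 instead reports a recommendation to give it at enrollment.

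**The concern.** A before-and-after measure describes the group period only if the before value sits close to the start of the group. Here the first woman's baseline may be weeks old on day 1 while the tenth woman's is fresh. The lag depends only on enrollment order and on how fast the others arrive.

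Distress that begins in the wait and persists will appear at follow-up as a rise from baseline. Staff must then judge whether the group caused it, with no K6 value at opening to help. The same applies to any shift in the spirituality items. Illicit opioid use after enrollment but before the group exists can be tabulated as relapse, and section 17.3.2.2 then describes engagement by relapse status.

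The rationale following the section 8.3.2 criteria explains the entry restrictions: "we want to ensure our participants are stable with respect to abstinence and currently receiving MOUD care". That stability is checked at screening, with a urine test covering 2-3 days, and not at opening.

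**Working it through.** The plan has no figure for the wait. Its only related figure is the two-month participation time, so that is checked first.

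**Stated timings**
- Group length: 30 days (section 10.3.5).
- Follow-up window: six weeks = 42 days (section 10.3.8).
- Two months: taken as 60-61 days.
- Group plus full window: 30 + 42 = 72 days, which is 11-12 days over two months with no wait at all.
- If follow-up falls on the last group day, 60 - 30 = 30 days (or 31) remain for waiting.

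**Illustrative waits.** The Phase 3 accrual rate is not given. Assume even accrual, with screening, baseline and enrollment on the same day. The wait for woman k is (10 - k) × the spacing between women. A later survey lengthens the screening-to-opening gap.

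| Assumed accrual | Waits | Mean | Wait over 30 days | First woman, screening to end of group |
|---|---|---|---|---|
| 2 per week | 4.5, 4.0, ..., 0 weeks | 2.25 weeks | 1 of 10 (31.5 days; the next is 28) | 31.5 + 30 = 61.5 days |
| 1 per week | 9, 8, ..., 0 weeks | 4.5 weeks | 5 of 10 (63, 56, 49, 42, 35 days) | 63 + 30 = 93 days |

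The first row just about fits two months if follow-up is immediate. The second does not, so it shows what slower accrual would do to the stated duration and is not the expected case.

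**What the wait does to each measure, at 2 per week**
- *K6 and spirituality.* The K6 asks about the past month. At follow-up on group day 30 it covers roughly the group itself, and at baseline the month before the survey. The wait, 0 to 31.5 days, lies between the two and is covered by neither.
- *TLFB.* With follow-up on group day 30, waits total 10 × 15.75 = 157.5 days and group days total 10 × 30 = 300. The share of since-screening days that precede the group is 157.5 / 457.5 = 34%. The daily record allows these to be separated, but no analysis section says that they will be.
- *UDS.* A 2-3 day test at screening describes day 1 only for a woman screened within about three days of opening. At a spacing of 3.5 days that is the tenth woman alone.

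**The case against.** The strongest reply is that little depends on this. The study is a single-arm beta test of ten women with descriptive analysis. K6 and spirituality change are not listed as primary, secondary or exploratory outcomes, and section 17.3.2 plans no analysis of them. Without a control group, change could not be attributed to the intervention even with a perfect baseline. All of that stands and limits the size of the point. It does not remove it, because section 10.3.8 states the purpose of the repeat measures and sections 11.2 and 18.19.1 act on K6 change.

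Several stronger readings are tempting, and the documents do not support them.
- *That the wait is wholly unbounded.* The two-month description is a soft bound. It is not written as a rule, and it conflicts with the plan's own 72 days.
- *That return to use in the wait is lost or necessarily blamed on the group.* The follow-up TLFB covers every day from screening, so the days are recoverable.
- *That early joiners are exposed before the group begins.* A welcome message follows joining, but section 10.3.4 says that the group has not begun and section 10.3.5 limits access to 30 days. No text says that members can post earlier. What is missing is only a statement of which days count toward engagement.
- *That inviting women after the survey bypasses clinician review.* Appendix B, section 2.0 E, says that a clinician or designee "will evaluate all pertinent screening and baseline assessments prior to participant enrollment". Under section 10.3.4 only women "completing the baseline survey, and accepting the invitation to join the Facebook group will be enrolled", so review can precede enrollment without contradiction.
- *That kits are given before baseline.* The section 10.3.4 wording permits this when the survey is deferred, while section 10.1.1 points to enrollment, which requires a completed survey. This is ambiguity to settle and does not establish a fault.
- *That safety in the wait is unwatched.* Appendix A starts adverse event assessment at consent, and section 11.1 tells women to report emergency visits, hospitalizations and overdoses at once.

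**Conclusion.** The point holds in a limited form. Individual baselines, a common start, no enforceable limit and no reassessment before day 1 mean that K6 and spirituality change includes a wait that must differ between women unless all ten are processed together. Relapse counted from enrollment can include use before the group opened.

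The size cannot be derived from the documents. At an assumed two women per week the mean lag is 2.25 weeks and 1 of 10 women waits over 30 days. Slower accrual would break the stated two-month duration. Recruitment, retention and satisfaction results are not affected by baseline lag. The change is worth making because K6 change has safety uses and these procedures are being tested for a later pilot RCT.

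**What to change.** 1. Set the opening date when the tenth woman enrolls, and take the K6 and spirituality items by phone in a short fixed window before it, say seven days. Sections 10.3.1.2 and 10.3.3 already allow a phone survey. Where the survey was done at the UDS visit, repeat only these items. Moving the whole survey into the window is an alternative, but because enrollment requires the survey, the opening trigger would then have to be reworded.
2. Give the smudge kit and journal only after the baseline survey, and reconcile section 10.3.4 with section 10.1.1.
3. State that engagement is counted on group days 1-30 only.
4. Report TLFB opioid and MOUD days separately for screening to opening and from opening onward, and say which of these periods the relapse summary uses.
5. Report each woman's days from screening and from baseline to opening.
6. Reconcile the two-month duration (Protocol Summary and section 6.3) with sections 10.3.4, 10.3.5 and 10.3.8.

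Whether anything learned before opening should affect a woman's entry is for the sponsor to reconcile with the section 8.3.2 criteria and their rationale.

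The cost is protocol wording and one short extra call for women surveyed early, with no new visit, sample or staff. A woman may be lost before opening, which matters because section 17.2.2.2 cites ten as the minimum for optimal engagement. That loss should be reported as a feasibility result.

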10.3.5. Study Intervention Administration

The Facebook intervention was described above in **Sections 10.1 and 10.2**. Participants will receive a welcome message when they join the group and a closing message when the group ends. The intervention will be accessible for a 30-day period. Participation in the intervention is entirely virtual and asynchronous, and available 24 hours a day/7 days a week so they can comment, react, and click on posts/links on their own time. The moderators will post one selection from the intervention content library once every 1-2 days and prompt group discussions as needed. Within the 30-day period, we may host up to 2 live guest speaker events. The guest speakers would be either a member of our research team that would present on a topic relevant to our content library posts or Native experts/Elders who are knowledgeable in opioid recovery and who are well-known and respected in the community.

Moderators will check in with the group every 1-2 days to interact with the participants, monitor adherence to group guidelines, and take actions such as removing inappropriate postings and misinformation if necessary.

